ClinicalTrials.gov Study Protocol and Statistical Analysis Plan

COMIRB Protocol #: 18-1528

ClinicalTrials.gov Identifier: NCT03789396

Project Title: Pilot Study of Targeted Normoxia in Critically Ill Trauma Patients

Version Date: 09/16/2019

**Statistical Analysis Plan included on page 12

COMIRB Protocol

COLORADO MULTIPLE INSTITUTIONAL REVIEW BOARD
[name] [contact] [contact]

Protocol #: 18-1528

Project Title: Pilot Study of Targeted Normoxia in Critically Ill Trauma Patients

Principal Investigator: **[name], MPH**

Version Date: 09/16/2019

Version 2

I. Hypotheses and Specific Aims:

Supplemental oxygen is fundamental in caring for critically ill trauma patients to enhance cellular energy production, optimize recovery, and maximize survival. While the avoidance of hypoxia is vital, the current clinical practice of excessive oxygenation in military and civilian settings is common, is unnecessary, and may even be harmful. Specifically, excessive oxygen supplementation promotes hyperoxic organ injury through pro-inflammatory reactive oxygen species and ischemic vasoconstriction. Indeed, hyperoxia has been shown to increase mortality in critically ill patients.

We convened a panel of 31 national and local experts in trauma surgery, critical care, and emergency medicine to define optimal oxygenation targets in critically ill trauma patients. The strong consensus was to target normoxia at an oxygen saturation (SpO₂) range of 90-96% and arterial oxygen (PaO₂) range of 60-100 mmHg. In addition, we performed a retrospective study of critically ill trauma patients at University of Colorado Hospital and found that hyperoxia (SpO₂ >96%) was present in the context of supplemental oxygen for more than half of the hospitalization. This identifies a discordance between current practice and expert consensus. The primary reason for this is convenience, as physician, nursing, and respiratory therapy leaders at University of Colorado Hospital all agree that targeting normoxia is optimal for patient care. Indeed, a similar normoxia strategy is already written into local clinical protocols (see attachment), yet is not well followed. Therefore, clinical leaders from Emergency Medicine, Trauma Surgery, Neurosurgery, and Critical Care at University of Colorado Hospital are increasing educational efforts to improve adherence to the established clinical guidelines for oxygenation in critically ill trauma patients.

Specific Aim:

We will conduct an observational pre/post study to evaluate the impact of these efforts to optimize oxygen delivery and oxygenation in critically ill trauma patients.

Hypotheses:

[figure not shown]
We hypothesize that the clinical efforts to improve adherence to oxygen guidelines will:

- a) improve the proportion of time spent with target normoxia thresholds (oxygen saturation [SpO_2] 90-96%) by
- b) reducing utilization of unnecessary supplementation oxygen
- c) without a substantive increase in hypoxic episodes or an adverse impact on clinical outcomes.

II. Background and Significance:

Oxygen therapy has undisputed importance in the care of critically ill medical and trauma patients to treat and prevent morbidity associated with hypoxia.^{1,2} However, generous supplemental oxygen is routine, and often results in hyperoxia.³⁻⁶ While there is no known benefit of excessive oxygenation, common clinical perception has been that this practice is safe and creates a margin of safety against hypoxia.⁷⁻⁹ However, evidence indicates that hyperoxia can also harmful. Here we summarize the rationale and relevance of the proposed research to avoid but hypoxia and hyperoxia and target normoxia.

[figure not shown]
Pre-clinical and observational data support the concept of targeted normoxia. There is a U-shaped relationship between oxygenation and mortality in critically ill patients, with both ends of the spectrum—hypoxia and hyperoxia—individually associated with higher mortality.^{10,11} Laboratory evidence has long demonstrated toxicity associated with hyperoxia through mitochondrial production of pro-inflammatory reactive oxygen species

ischemic vasoconstriction that leads to tissue damage and vital organ injury.¹²⁻¹⁴ **Figure 1** summarizes the underlying cellular mechanisms for balance between the beneficial and harmful effects of oxygen therapy.

Figure 1. Beneficial (green arrows) and deleterious (red arrows) effects of oxygen therapy during circulatory shock. *Adapted from Asfar P et al. Intensive Care Med 2015;41:1118.*

[figure not shown]
Numerous observational cohort studies have demonstrated an association between hyperoxia and higher mortality broadly in intensive care unit patients and in specific subpopulations, such as cardiac arrest, myocardial infarction, ischemic stroke, and

traumatic brain injury.^{2,15} Prehospital hyperoxia can also have an important impact on clinical outcomes.¹⁶ In a recent meta-analysis, hyperoxia (compared to normoxia) was associated with a 21% higher odds of mortality across a broad range of critical illness, even after adjusting for baseline characteristics and illness severity (Figure 2).¹⁵

Figure 2. Adjusted associations between arterial hyperoxia and hospital mortality overall and by subsets of critical illness.¹⁵

[figure not shown]
Clinical trial evidence also supports the safety and potential efficacy of targeted normoxia. Panwar et al. recently published the first randomized controlled trial to compare different oxygen targets in critically ill patients, comparing a target oxygen saturation (SpO_2) 88-92% (“conservative”) vs. $\geq 96\%$ (“liberal”/conventional).¹⁸ In this multicenter pilot trial (4 intensive care units [ICU] in Australia/New Zealand; $n=103$), targeted normoxia (conservative group) safely reduced the amount of supplemental oxygen administered (mean $\text{FiO}_2 > 10\%$ lower in the conservative group during the first 7 days; **Figure 3**) and duration of time in the hyperoxic range (4% conservative vs 22% liberal) without an increase in time spent with $\text{SpO}_2 < 88\%$ (0.3% conservative vs 1% liberal). In this small, underpowered trial, clinical outcomes (organ dysfunction, hospital length of

stay, mortality) were not statistically different between groups. However, there were promising signals for targeted normoxia reducing 90 day mortality (adjusted hazard ratio 0.77 [95%CI, 0.40-1.50]), especially in the pre-specified subgroup with acute lung injury (adjusted hazard ratio 0.49 [95%CI, 0.20-1.17]).

Figure 3. Percentage of time spent at each SpO_2 level (A) and treatment separation for SpO_2 (B), PaO_2 (C), and FiO_2 (D) targeted normoxia (conservative oxygen) and relative hyperoxia (liberal oxygen) arms in Panwar trial.¹⁸

Girardis et al. similarly compared a targeted normoxia strategy (arterial oxygen pressure [PaO_2] 70-100 mmHg or SpO_2 94-98%) to a conventional (relative hyperoxic) strategy ($\text{PaO}_2 \geq 150$ mmHg or $\text{SpO}_2 \geq 97\%$) in a single Italian ICU ($n=434$).¹⁰ The targeted normoxia group had substantially lower ICU mortality (11.6% vs. 20.2% in the conventional group; $p=0.02$; **Figure 4**) and a lower incidence of hospital mortality (24.2%

33.9%; $p=0.03$), shock (3.7% vs. 10.6%; $p=0.006$), and duration of mechanical ventilation (mechanical ventilation free hours 72 vs. 48; $p=0.02$). Collectively, these two trials provide strong rationale for the feasibility, safety, and potential efficacy for a targeted normoxia strategy in critically ill trauma patients.

Figure 4. Probability of survival through day 60 for the targeted normoxia and conventional (relative hyperoxia) arms in the Girardis trial.¹⁰

Additional clinical trial evidence in other populations suggests that targeting either hypoxia or hyperoxia may be harmful. In three high-profile randomized trials of pre-term infants, permissive hypoxia (SpO_2 85-89%) was associated with a higher mortality and disability.¹⁹⁻²¹ The applicability of these trials to critically injured adults is unknown; however, we propose a normoxia, rather than permissive hypoxia, strategy. Similarly, five trials of clinical trials have demonstrated worse clinical outcomes of hyperoxia in non-critical trauma,²² abdominal surgery,²³ myocardial infarction,²⁴ septic shock (NCT01722422), and ischemic stroke (NCT00414726) patients. Therefore, the prehospital, emergency, and critical care communities now recommend careful titration to **normoxia** to avoid hypoxia and preserve tissue oxygenation while preventing iatrogenic hyperoxia.^{25,26}

Implementation of targeted normoxia is desirable, safe, and feasible. Prehospital, emergency, trauma, and critical care physicians now firmly believe that avoidance of hypoxia and hyperoxia are both important and that oxygen titration should be practiced in critically ill patients.^{27,28} Several implementation studies demonstrate that oxygen titration based on non-invasive oxygen saturation can be safely protocolized to achieve normoxia,^{25,26,29} and markedly reduce consumption of supplementary oxygen.^{4,18} Accordingly, targeted normoxia is now widely accepted as standard care in emergency departments and ICUs.¹²⁻¹⁴ For example, ARDS Network oxygenation targets (SpO_2 88-95%) has been widely accepted for patients with and without ARDS.³⁰ Yet, widespread use of excessive oxygenation persists in routine care in the prehospital setting, emergency departments, and ICUs with over 75% of patients exposed to prolonged periods of hyperoxia.^{12,31}

III. Preliminary Studies/Progress Report:

We conducted a Delphi consensus process enlisting panel of 31 national and local experts in trauma surgery, critical care and emergency medicine.

We asked the expert panel to rate how strongly they agreed or disagreed with specific SpO2 low thresholds, SpO2 high thresholds, PaO2 low thresholds and PaO2 high thresholds. Based off our analysis of the data, we were able to identify what the majority of experts felt were appropriate oxygenation thresholds. Initial votes are summarized in Figures 4-7 below.

Figure 4: Agreement with Lower SpO2 Thresholds in Delphi Stage 2

[figure not shown]

Figure 5: Agreement with Higher SpO2 Thresholds in Delphi Stage 2

Figure 6: Agreement with Lower PaO2 Thresholds in Delphi Stage 2

[figure not shown]
[figure not shown]

Figure 7: Agreement with Higher PaO2 Thresholds in Delphi Stage 2

For these data, we proposed an SpO₂ range of 90-96%, PaO₂ range of 60-100 mmHg. In the Final Delphi Stage, we asked our expert panel for a final yes/no vote on these thresholds to confirm final consensus on oxygenation in critically ill trauma patients. Voting was as follows, which confirmed our final target ranges (>80% agreement was pre-defined as consensus):

- ▶ Low SpO₂ threshold = 90%
 - 89% agreement
- ▶ High SpO₂ threshold = 96%
 - 89% agreement
- ▶ Low PaO₂ threshold = 60 mmHg
 - 96% agreement
- ▶ High PaO₂ threshold = 100 mmHg
 - 89% agreement

These thresholds are concordant with existing clinical guidelines at University of Colorado Hospital, and the data from the expert consensus process has provided additional motivation for clinical leadership to improve their adherence to guidelines. In an observational study design, we will evaluate the impact of clinical efforts to improve guideline adherence.

III. Research Methods

A. Outcome Measure(s):

For the primary feasibility outcome, we will assess oxygenation, as measured by SpO₂ and PaO₂, relative to amount of supplementation oxygen during the first 7 days. For ventilated

patients, supplemental include fraction of inspired oxygen (FiO_2), positive end expiratory pressure, ventilator mode, mean airway pressure, and tidal volume. With this information we can calculate both P/F ratio and oxygenation index. For non-ventilated patients, we will collect volume and route of supplemental oxygen. These data will be used to longitudinally calculate the observed oxygenation compared to the defined oxygenation targets (SpO_2 90-96% and PaO_2 60-100 mmHg). In addition, we will calculate the duration of hyperoxia time ($\text{SpO}_2 > 96\%$ or $\text{PaO}_2 > 100$ mmHg, unless no supplemental oxygen is delivered), and number/duration of hypoxia episodes ($\text{SpO}_2 < 88\%$ or $\text{PaO}_2 < 60$ mmHg, unless FiO_2 is 100%).

Although this pilot study will be underpowered for clinical outcomes, we will measure in-hospital mortality, ventilator-free days, duration of supplemental oxygen, acute organ injury (as measured by daily Sequential Organ Failure Assessment [SOFA] scores over 7 days), intensive care unit length of stay, hospital length of stay, and hospital disposition (facility vs. home).

B. Description of Population to be Enrolled and C. Study Design and Research Methods

We will conduct a pilot study to inform a future larger scale implementation study across multiple trauma centers to test the clinical effectiveness of the targeted normoxia strategy. In the proposed pilot study, we will test and optimize feasibility and potential for effectiveness.

Study Design and Setting: This study will be an observational before-after study conducted at the University of Colorado Hospital.

Participants: We will compare oxygenation and outcomes trauma patients admitted to the ICU during the 6 months after the clinical implementation to similar patients during the same 6 months in the prior year (to adjust for seasonal effects) and the immediate preceding 6 month period (to minimize potential for secular trends).

The clinical implementation of normoxia guidelines is part of standard care and therefore there is no specific research intervention. While the research team will help the clinical leadership with education of clinical staff, the research team will have no interactions with patients or surrogates. Patient care will occur per treating clinicians, including decisions on when to adhere and not to adhere to the guidelines on normoxia. The research procedures will be observational, retrospective data collection. We will collect data on patients with acute injury that are admitted from the emergency department to the surgical-trauma or neurosurgical intensive care units.

D. Description, Risks and Justification of Procedures and Data Collection Tools:
The risks of this research are related to retrospective data collection and interviews as below.

Identifiers

Human subjects will be identified based on the unique hospital encounter number that is specific to the exact hospitalization for an individual patient. Additional identifiers will be temporarily collected (medical record number and date of birth) to ensure proper matching for electronic data collection and to facilitate manual chart review when needed. These identifiers will be removed from the dataset as soon as the database is cleaned and closed for analysis (thereby creating a completely de-identified dataset thereafter).

Confidentiality

Privacy and confidential of human subjects and study data are of utmost importance. We will collect, manage, and store protected health information data using a REDCap database developed for this study, in collaboration with the Colorado Clinical and Translational Sciences Institute. Data will be collected using Health Data Compass and verified by manual chart review. REDCap is a secure and encrypted web application designed to support data capture for research studies, providing user-friendly, web-based case report forms, real-time data entry validation (e.g. for data types and range checks), audit trails and a de-identified data export mechanism to common statistical packages (SPSS, SAS, Stata, R/S-Plus). The system was developed by a multi-institutional consortium which includes University of Colorado Denver and was initiated at Vanderbilt University. The database is hosted at the University of Colorado Denver Development and Informatics Service Center, which will be used as a central location for data processing and management. REDCap is considered more secure than applications such as Survey Monkey and programs such as Microsoft Excel or Access; therefore, it is the preferred data collection, management, and storage modality preferred by our Colorado Multiple Institutional Review Board.

Identifiers will be destroyed as soon as no longer required, typically after data cleaning is complete and database is closed for analysis. IRB-approved study investigators and coordinators will have access to study data; because this study is sponsored by the Department of Defense, we will make allowances for United States Army Medical Research and Material Command (USAMRMC) to be eligible to review study records if needed. We do not anticipate collecting sensitive information (purposefully or inadvertently); however, state and federal regulations will be followed relating to mandatory reporting requirements and study staff are trained appropriately.

Disposition of data

Electronic data will be stored on University servers or on password-protected/encrypted computers that are behind the University firewall. We do not anticipate any hard copy data, but should be generated, they will be secured in a locked file cabinet in a locked office. Data will be stored for as long as IRB and DOD regulations recommend, whichever is longer (typically 5 years). A limited de-identified dataset will be archived long-term for future use by the local investigators and the general research community. The proposed research does not interface with the FDA, and thus, there are no special requirements relating to disposition of data.

E. Potential Scientific Problems:

The biggest challenge to the research will be the extent to which guideline adherence is improved during the study period.

There can also be challenges with electronic data collection with Health Data Compass. However, we have worked closely with Compass in the preparatory work (COMIRB #17-1359), and also will supplement electronic data collection with manual chart review as needed.

F. Data Analysis Plan:

We will model continuous SpO₂ and PaO₂ data separately and a third model where both are combined. The SpO₂ model will have the most field relevance but incorporating the PaO₂ data will be useful in applying results to the hospital setting in future implementation trials. Specific attention will be paid to the defined normoxia target range, as well as short-term episodes of hypoxia or hyperoxia. Oxygenation and oxygen supplementation data will be analyzed descriptively.

Clinical outcomes will be analyzed descriptively to compare the pre- and post-periods. We will also adjust for a limited number of covariates (eg, injury severity) to reduce risk of confounding. However, we fully recognize that the primary purpose of this pilot intervention is feasibility and safety, and so clinical outcomes will be underpowered.

G. Summarize Knowledge to be Gained:

The proposed pilot study will help us to understand the feasibility, barriers, and facilitators for improving oxygenation practices in critically ill trauma patients. The results will provide valuable preliminary data for planning a large multicenter implementation trial to evaluate the impact of this intervention on clinical outcomes and safety. These data collectively will provide actionable data to improve care of critically injured civilians and military service members.

H. References:

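### Does the time-in-range measure need a rule for room-air time with SpO2 above 96%?

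*Combined protocol and SAP*

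**What the plan says.** Section I states hypothesis (a), that the effort will "improve the proportion of time spent with target normoxia thresholds (oxygen saturation [SpO_2] 90-96" (per cent). It names hypothesis (b) as the means: "reducing utilization of unnecessary supplementation oxygen". Neither sets a denominator or an oxygen condition for (a).

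Under Research Methods, A. Outcome Measure(s), the primary feasibility outcome is oxygenation assessed "relative to amount of supplementation oxygen during the first 7 days". The data will be used to "longitudinally calculate the observed oxygenation compared to the defined oxygenation targets", with the target given as SpO2 90-96% and PaO2 60-100 mmHg, again without an oxygen condition. The section then adds a separate measure, hyperoxia duration, in which SpO2 above 96% or PaO2 above 100 mmHg counts "unless no supplemental oxygen is delivered". That exemption is attached to hyperoxia only. For patients not on a ventilator, "we will collect volume and route of supplemental oxygen".

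F. Data Analysis Plan models continuous SpO2 and PaO2, separately and together, and says: "Oxygenation and oxygen supplementation data will be analyzed descriptively". It gives no formula for time in range.

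**The concern.** The plan expects (a) to improve through (b). Suppose unneeded oxygen is stopped and the patient stays above 96% on room air. Oxygen use falls and hyperoxia duration falls, but time in range does not rise if that time is counted as out of range. If an analyst drops room-air time above 96% from the denominator, or counts it as acceptable, the same change in care gives a larger gain. In a before-after study with retrospective data collection, a choice like this could be made after the results are seen.

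At stake is how clearly one feasibility figure can be read when it is carried into planning the larger multicenter study. Section I reports that hyperoxia on supplemental oxygen filled more than half of the hospitalization, so the amount of time that could move is not small.

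**Working it through.** The documents give no time-in-range figure, effect size or sample size, so there is no stated figure to reproduce. The check asks how far the possible rules differ.

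**Categories (percent of SpO2 time).** T = 90-96%; H = above 96% on oxygen; R = above 96% on room air; L = below 90%. These sum to 100.

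**Rules.** A: T over all time. B: T / (100 − R), with room-air time above 96% excluded. C: T + R, with that time counted as acceptable.

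**Inputs.** H = 50 is the floor of the more-than-half figure in section I, which refers to the hospitalization and not to the first 7 days. T = 35, R = 10 and L = 5 are assumptions. So is the change: 25 points leave H, a fraction f goes to R and the rest goes to T.

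**Formulas.**
- A: 35 to 35 + 25(1 − f), so the gain is 25(1 − f).
- B: 35/90 = 38.89% to (60 − 25f)/(90 − 25f).
- C: 45 to 70, so the gain is 25 for every f.
- Hyperoxia: 50 to 25, a fall of 25 for every f.

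| f | Gain, A | After, B (%) | Gain, B | B − A | Gain, C |
|---|---|---|---|---|---|
| 0 | 25.00 | 66.67 | 27.78 | 2.78 | 25 |
| 0.25 | 18.75 | 64.18 | 25.29 | 6.54 | 25 |
| 0.5 | 12.50 | 61.29 | 22.40 | 9.90 | 25 |
| 1 | 0 | 53.85 | 14.96 | 14.96 | 25 |

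A second set of assumptions (H = 52, T = 30, R = 15, L = 3; 15 points moved, f = 0.5) gives A 30.0 to 37.5 (+7.5), B 35.3 to 48.4 (+13.1) and C 45 to 60 (+15.0).

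**When the rules agree.** If R = 0 in both periods, B = T/100 and C = T, so all three coincide. The documents do not report R, and nothing in them places this study between that case and f = 1.

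**Would rule C add information?** T + R = 100 − H − L. Its change is the fall in H minus any rise in L, so it largely repeats the SpO2 part of hyperoxia duration.

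**Would another rule be safer?** Suppose case mix alone shifts 10 points from H to R, with no change in care. Then A: 35 to 35 (0). B: 35/90 to 35/80, or 38.89% to 43.75% (+4.86). C: 45 to 55 (+10). H: 50 to 40 (−10). True weaning of 10 points with f = 1 gives the same four changes. Rules B and C therefore rise without any improvement in practice, and setting one measure beside another does not separate the two causes.

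**Which rule does the text support?** SpO2 of 98% on room air is not within 90-96%, and (a) carries no oxygen condition, so the wording gives rule A. The phrase "relative to amount of supplementation oxygen during the first 7 days" describes looking at oxygenation alongside oxygen dose and does not remove room-air time from a denominator. Nothing says that target time, hyperoxia and hypoxia must together account for all time. One measure can record the saturation attained and the other avoidable oxygen excess.

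**The case for a change.** The strongest case for a change is that one sentence would settle the matter at no cost. The oxygen data are already collected, and the hyperoxia exemption shows that the authors did not regard high saturation on room air as hyperoxia. Someone could cite that exemption to defend rule B or C after seeing the data, and (a) is the first hypothesis listed.

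Part of this stands. The plan does not classify this time expressly, and under rule A the measure can miss successful weaning. A report that shows room-air time above 96% beside the in-range proportion would be easier to read.

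The rest is weaker. The one-sentence addition would confirm rule A, which the wording already gives. Calling rule A an understatement presumes that room-air time above 96% is a success for (a). The documents only decline to call it hyperoxia. A fuller remedy that added rule C as a supplementary measure would mostly restate hyperoxia duration. Extending the covariate adjustment to oxygenation is a separate matter. The plan says "We will also adjust for a limited number of covariates (eg, injury severity) to reduce risk of confounding" in its paragraph on clinical outcomes, and adjustment would not decide how room-air time is classified.

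**Conclusion.** No change to the plan follows. This is a missing detail with a sensible default: the plain 90-96% proportion over all observed SpO2 time in the first 7 days. That default is also the only one of the three rules that does not rise under the case-mix shift shown above.

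The effect of the choice cannot be sized from the documents. The 2.8 to 15.0 point spread rests on assumed time shares, and its upper end requires all the removed hyperoxic time to move to room air and all of it to stay above 96%. Even there, hyperoxia duration falls by the full 25 points, so the weaning would be visible in the planned summaries. The continuous SpO2 and PaO2 models give a further view that does not depend on the cut at 96%.

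The conclusion rests on three features of the plan: oxygenation is analysed descriptively, no test or go/no-go rule uses (a), and oxygen use and hyperoxia duration are summarised in their own right. If a later trial made time in range a formal endpoint, the classification of room-air time would need to be fixed in advance.

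### The 7-day hypoxia measure has no end point at transition to comfort care, so monitored desaturation after support is withdrawn counts in the measure behind hypothesis (c)

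*Combined protocol and SAP*

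**What the plan says.** Section III.A (Research Methods, Outcome Measure(s)) assesses oxygenation "relative to amount of supplementation oxygen during the first 7 days". It defines the safety quantity as the "number/duration of hypoxia episodes", with hypoxia at SpO2 below 88% or PaO2 below 60 mmHg. The one exemption is the closing condition "mmHg, unless FiO_2 is 100" per cent. Hyperoxia has a parallel exemption: high readings do not count when no supplemental oxygen is being given.

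Sections III.B and C take in "patients with acute injury that are admitted from the emergency department to the surgical-trauma or neurosurgical intensive care units" and list no exclusion criteria. The comparison is between the 6 months after implementation and two earlier 6-month periods.

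Hypothesis (c) in Section I predicts improvement "without a substantive increase in hypoxic episodes or an adverse impact on clinical outcomes". Section III.F says "Oxygenation and oxygen supplementation data will be analyzed descriptively" and promises specific attention to the target range "as well as short-term episodes of hypoxia or hyperoxia". It does not say which readings are left out. The covariate adjustment it mentions sits in the paragraph on clinical outcomes.

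Comfort care, withdrawal of support and brain death are not mentioned anywhere. No rule says when the window closes for a patient who dies before day 7.

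**The concern.** Hypothesis (c) reads hypoxia as a possible harm of titrating oxygen downwards. Desaturation after a decision to withdraw support reflects that decision and not the titration. A patient then breathing room air or low-flow oxygen does not meet the FiO2 100% exemption, so the rule counts those hours.

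The study is meant to supply feasibility and safety data for a larger multicentre study. If hypoxia is uncommon otherwise, a few terminal episodes can make up a visible part of the total. A change between periods in how many patients reach comfort care within a week, or in how long they stay monitored afterwards, could then look like harm from the programme or mask it.

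**Working it through.** **Reading the rule.** The plan states no expected hypoxia rate, margin or sample size, so there is no figure of its own to reproduce. The first step is to put a monitored patient on room air, after withdrawal of support on day 3, through the text:

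- Population: included, since no exclusion applies.
- Window: day 3 lies within the first 7 days, and nothing closes it.
- Threshold: SpO2 below 88% is met.
- Exemption: FiO2 is not 100%, so it does not apply.
- Analysis: Section III.F has no truncation or sensitivity rule for such readings.

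The reading counts, both as an episode and as time.

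**Scale of the background.** Section II reports time with SpO2 below 88% in a cited pilot randomised trial as "0.3% conservative vs 1% liberal". Over a full window of 7 × 24 = 168 h:

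- 0.003 × 168 = 0.504 h per patient
- 0.01 × 168 = 1.68 h per patient

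These are borrowed figures. That trial enrolled mechanically ventilated patients and used other targets, so they serve for scale only.

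**Added time.** Let f be the share of patients with monitored terminal desaturation in the window and h its length in hours. The mean added per patient is f × h. Neither value is in the documents, so what follows is assumed.

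- Level, f = 5% and h = 4 h: 0.05 × 4 = 0.20 h, which is 0.20/1.68 = 12% to 0.20/0.504 = 40% of background.
- Level over a wide range, f = 2% to 10% and h = 1 to 12 h: 0.02 to 1.2 h per patient.

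**Added pre/post difference.** With the same h in both periods this is (f_post − f_pre) × h.

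| f_pre | f_post | h | Added difference | Relative to 1% background | Relative to 0.3% background |
|---|---|---|---|---|---|
| 5% | 5% | any | 0 h | 0% | 0% |
| 4% | 6% | 4 h | 0.08 h | 5% | 16% |
| 5% | 9% | 3 h | 0.12 h | 7% | 24% |

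In absolute terms 0.12 h is about 7 minutes, or 0.12/168 = 0.07 percentage points. If monitors are removed at withdrawal, h is near zero and so is every entry.

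**Episodes.** Each such patient adds at least one episode, however short. A shift from 5% to 9% therefore adds at least 0.09 − 0.05 = 0.04 episodes per patient. The documents give no background episode rate to set this against.

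**Denominator.** The plan does not say whether hypoxia will be summarised in hours or as a share of each patient's observed time. The choice matters for early deaths: 3 h is 3/168 = 1.8% of a full window but 3/24 = 12.5% for a patient who dies at 24 h.

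**The case against.** The strongest case against is that the point rests on silence and on assumed numbers. The plan does not say that these patients' terminal hours are kept; it gives no rule either way. Shares and durations are invented for scale, and the percentages look large because a small borrowed background sits in the denominator. That background may already contain terminal hours, since the cited trial had deaths, so adding to it may double count. The study is a descriptive pilot with no margin or test for hypothesis (c), so no formal decision is distorted. Truncation has its own risk: if hypoxia led to the comfort-care decision, ending the window there is informative.

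Most of this stands as a limit on size. It does not remove the point, because Section III.A gives a working definition with one stated exemption, and applying it as written counts these hours. The informative-truncation worry is met by counting all hypoxia before the order and showing the untruncated figures alongside.

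Three stronger readings are tempting, and the documents do not support them:

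- **That the pre/post comparison is biased.** It is biased only if the share or duration of terminal desaturation differs between periods. Equal values leave the absolute difference unchanged.
- **That brain-dead patients add terminal desaturation.** The documents do not say whether support or charting continues after declaration. If it does, the hours would fall mainly into hyperoxia or on-target time, which is a different outcome, and no size can be put on it.
- **That 0.3% to 1% is this cohort's background.** It comes from ventilated patients in another trial, while this cohort includes non-ventilated patients.

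**Conclusion.** The point holds as a gap in the outcome definition. Monitored desaturation after withdrawal of support, on less than 100% oxygen, counts as hypoxia under Section III.A, and nothing elsewhere takes it out. The sure consequence, if any such patients are monitored, is a higher level and more noise in the safety measure. Bias in the pre/post contrast is conditional on a difference between periods, which an unrandomised design does not rule out.

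The size is unknown. The example of 0.12 h per patient (7% to 24% of the borrowed background) rests on an assumed rise in such deaths from 5% to 9%, 3 h of monitored desaturation each, and a full 168 h window. Local monitoring practice could bring it close to zero. This is a cheap improvement to a safety measure and not a flaw that undermines the study.

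**What to change.** In Section III.A, end each patient's oxygenation window (on-target, hyperoxia and hypoxia time) at the earliest of the comfort-care order, death, or the end of day 7. As a secondary point, apply the same cut-off at declaration of brain death, where the effect would be mainly on hyperoxia and on-target time. Hypoxia before the cut-off still counts. Keep all these patients in mortality and the other clinical outcomes.

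Report by period the number of patients truncated and, as a sensitivity row, the untruncated hypoxia counts and durations. This is a data-handling rule and changes nothing in patient care. It extends the logic of the two exemptions already in Section III.A, which set aside readings that titration could not have changed.

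The cost is a sentence or two in the plan and one date and time per affected patient, taken in the manual chart review that Section III.D already describes. It must be captured before the identifiers are removed at database close, because the charts cannot be revisited afterwards. There are two downsides. Order times can be imprecise, and truncation may be informative if earlier hypoxia prompted the decision; the untruncated row is there for that reason.
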